1.7 Reproductive Health Related Endocrine Disruption in Cancer Care

Rev. Add10

We propose a 2-year observational study following tumor markers for fertility status and endocrine disruption of the first 200 individuals who agree to participate.

Primary Hypothesis

At least 80% of females will have significant endocrine disruption during chemotherapy.

Background

The sequelae of endocrine disruption may include loss of fertility. Although some cancer therapy modalities induce amenorrhea, many patients undergoing treatment remain fertile. After a short period of chemotherapy-induced amenorrhea, 50% of females younger than 35 years resume menstruation, whereas in older females the risk of amenorrhea is increased due to reduced follicular reserve.⁹ The absence of menstruation does not necessarily indicate lack of ovarian function. Additionally, the possibility of spontaneous recovery of ovarian function has been observed, particularly in cases of ovarian germ cell cancer. A study by Fossa found that cisplatin-based chemotherapy is followed by a recovery of ovarian function in almost all patients.⁹

For patients on chemotherapy who desire fertility, ovarian function should be reassessed periodically. Since menstrual activity is not a reliable index to assess ovarian function, various tests like FSH level, inhibin A or B levels or antimullerian hormone (AMH) and vaginal ultrasonography assessment for number of antral follicles can be used.¹⁰

Knowledge of the functional ovarian reserve may benefit females with cancer prior to making important decisions regarding treatment, fertility preservation, and contraception. An ideal marker for fertility status has not yet been identified. Recent literature (2009) indicates the best biochemical indicators of ovarian reserve are serum FSH levels, AMH and Inhibin B.¹¹ In the reproductive

endocrinology literature, AMH is emerging as the optimal marker to determine ovarian reserve and subsequent pregnancy success.¹² Experience with AMH in cancer survivors is limited, however this marker has potential as an indicator of ovarian function post chemotherapy.^{11,13} FSH as a marker may be less reliable as it is ovulatory cycle dependent and affected by tamoxifen and other hormonal therapies.¹³

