3.1 Eligibility Criteria

Rev. 11/17	_____ 3.1.1	Female patients presenting with initial diagnosis of any type of cancer, including patients with DCIS.
Rev. Add8	_____ 3.1.2	Patients must not have initiated chemotherapy, radiation therapy or endocrine therapy prior to registration to this study.
Rev. 11/17	_____ 3.1.3	Patients must not have had a prior hysterectomy, bilateral oophorectomy or sterilization of any method.
Rev. Add9	_____ 3.1.4	Patients must be pre-menopausal patients within the reproductive age range of 15-55 years. Please note, pre-menopausal will be defined as females meeting the following criteria: 
• Patients not currently on hormonal contraception with the presence of menses in the past 6 months.• If no menstruation in the past 6 months, without hormonal manipulation, then confirmed FSH < 23mIU/mL• If age < 47 years and on hormonal contraception, then patient will be eligible regardless of menstrual history• If age ≥ 47 years and on hormonal contraception, then FSH confirmed < 23mIU/mL
Rev. Add10	_____ 3.1.5	Pregnant females are eligible to participate in this study.
Rev. Add10	_____ 3.1.6	Patients must have the cognitive ability to participate in the study.

Rev. 11/17 4. CTEP Registration Procedures

Rev. Add8
Rev. Add11

Food and Drug Administration (FDA) regulations and National Cancer Institute (NCI) policy require all individuals contributing to NCI-sponsored trials to register and to renew their registration annually. To register, all individuals must obtain a Cancer Therapy Evaluation Program (CTEP) Identity and Access Management (IAM) account (<https://ctepcore.nci.nih.gov/iam>). In addition, persons with a registration type of Investigator (IVR), Non-Physician Investigator (NPIVR), or Associate Plus (AP) must complete their annual registration using CTEP's web-based Registration and Credential Repository (RCR) (<https://ctepcore.nci.nih.gov/rcr>).

RCR utilizes five person registration types.

- IVR — MD, DO, or international equivalent;
- NPIVR — advanced practice providers (e.g., NP or PA) or graduate level researchers (e.g., PhD);
- AP — clinical site staff (e.g., RN or CRA) with data entry access to CTSU applications (e.g., Roster Update Management System (RUMS), OPEN, Rave,);
- Associate (A) — other clinical site staff involved in the conduct of NCI-sponsored trials; and

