8.6.3 Plan for Endocrine Disruption in Cancer Care

Rev. Add11

A longitudinal observational study is proposed to examine reproductive health biomarkers in a subgroup of participants (first 200 subjects who agree to participate in this part of study) in the EROS Trial. Participants will be asked to provide blood samples for laboratory correlates (AMH, FSH, TSH, TPO), indicating reproductive health, fertility status, and endocrine disruption. Blood samples will be obtained at baseline and periodically at 3, 6, 12, and 24 months from baseline visit on the study, which totals 8 blood draws. In addition, blood samples will be acquired in conjunction with chemotherapy (within one week of each regimen, prior to chemotherapy) or radiation therapy (within one week prior to the initiation of radiation therapy then every four weeks until the end of radiation treatment). This will increase the number of samples for that population as we attempt to

assess impact of chemotherapy on endocrine function. The hormonal levels at each measurement point will be summarized (by median and range) and plotted across time by marker. All analysis will be performed for patients with chemotherapy and without chemotherapy separately. To assess the impact of chemotherapy on endocrine function, a linear mixed-effect model will be used to make comparisons between the two groups with respect to each marker.

To determine the percent of females having significant endocrine disruption during chemotherapy, Table 7 below summarizes the abnormal level for each marker.

Table 7: Endocrine Markers and Associated Threshold Values for Endocrine Disruption

Marker	Age Range	Abnormal Range
FSH	15-55	≥ 23.0 mIU/mL
TPO	15-55	< 35 IU/mL
TSH	≤ 19	0.50-4.30 mIU/mL
	≥ 20	0.40-4.50 mIU/mL
AMH	≤ 19	0.76 – 11.34 ng/mL
	20-29	0.76- 11.34 ng/mL
	30-39	< 9.24 ng/mL
	40-49	< 4.50 ng/mL
	≤ 50	< 0.45 ng/mL

Quest Diagnostics Laboratory reference ranges

For each marker, the patient with the observed lab value falling into the abnormal range is considered to represent a case with endocrine disruption. Frequency and percentage (along with its 95% confidence interval) will be used to summarize patients with endocrine disruption during chemotherapy for each marker.

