9.2 Sample Submission Schedule

Blood samples are being collected for the correlative studies outlined in Section [1.7](#) and analyzed by Quest Diagnostics.

NOTE: Results of these laboratory tests will not be returned to the institutions or reported to the patient.

NOTE: Blood samples should be collected as outlined in the table and sections below.

Rev Add 11

Biological Materials	Day of Registration [prior to treatment] ¹	Within One Week Prior to Start of Each Chemotherapy Regimen or Every Four Weeks during RT ¹	At the end of 3, 6, 12, 24 Months from Baseline Visit

From Patients Who Answer "Yes" to "I agree to participate in the laboratory research studies that are being done as part of this clinical trial."³
			
Serum (one 7.5mL red top tube) ²	X	X	X
Serum, SST (one 7.5mL red/black top) ²	X	X	X

1. For patients undergoing chemotherapy, blood samples will also be collected in conjunction with chemotherapy within one (1) week prior to the start of each chemotherapy regimen. For patients undergoing radiation therapy (RT) alone, blood samples will be collected within one (1) week prior to the initiation of radiation therapy and every four (4) weeks until the end of radiation treatment.
2. When possible, blood draws will be timed with the collection of blood draws for routine clinical purposes thus minimizing participant burden.

Rev. 5/17

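### The FSH disruption count and the FSH chemotherapy contrast ignore hormonal state at the draw, although the protocol itself says hormonal therapy and cycle affect FSH

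*Combined protocol and SAP*

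**What the plan says.** Section 8.6.3 plans marker summaries in the "first 200 subjects who agree to participate in this part of study". Table 7 gives FSH a single abnormal range, 23.0 mIU/mL or above, for ages 15-55. The case rule is that "the patient with the observed lab value falling into the abnormal range is considered to represent a case with endocrine disruption". For each marker, the percentage with disruption during chemotherapy is reported with a 95% confidence interval. All analyses are done separately for patients with and without chemotherapy, and a linear mixed-effect model compares the two groups on each marker. No covariate, exclusion, stratum or sensitivity analysis for hormonal state or cycle phase is named.

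The hypothesis in section 1.7 is: "At least 80% of females will have significant endocrine disruption during chemotherapy". The same section says: "FSH as a marker may be less reliable as it is ovulatory cycle dependent and affected by tamoxifen and other hormonal therapies".

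Section 3.1 sets who can be sampled:
- "If age < 47 years and on hormonal contraception, then patient will be eligible regardless of menstrual history".
- "Pregnant females are eligible to participate in this study".
- "Patients must not have initiated chemotherapy, radiation therapy or endocrine therapy prior to registration to this study". Nothing in the criteria restricts endocrine therapy afterwards.

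Draws are scheduled at registration, before each chemotherapy regimen or every four weeks during RT, and at 3, 6, 12 and 24 months. Within that schedule, where possible, "blood draws will be timed with the collection of blood draws for routine clinical purposes" (section 9.2). The test requisition in section 9.3.3 asks for date, time and fasting status, but not hormone use or cycle day.

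**The concern.** The protocol names a reason why FSH may mislead, admits patients to whom that reason applies, and then scores their values as if it did not apply. Two results are exposed.

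The first is the FSH percentage. A value moved across 23.0 by a hormonal agent is counted as disruption, or as its absence, whatever chemotherapy has done.

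The second is the chemotherapy contrast. If hormonal exposure differs between patients with and without chemotherapy, the FSH difference partly measures that exposure. The exposure varies with time, because endocrine therapy can begin only after registration and contraception can start or stop during follow-up. Adjusting for age or the baseline value would not remove it.

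**Working it through.** **No plan figure to reproduce.** The documents give no sample size, power or error rate for the endocrine sub-study beyond the target of 200. The check is a reading of the passages together, followed by an illustration of scale.

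**Step 1: the rule against the caveat.** Section 1.7 lists cycle, tamoxifen and other hormonal therapies as influences on FSH. The FSH row of Table 7 is conditional on none of them.

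**Step 2: the same cut-off elsewhere.** Section 3.1 also uses FSH at 23 mIU/mL, but there it depends on hormonal state. It applies to patients without recent menses only when there is no hormonal manipulation, and contraception users have their own rules split at age 47. Section 8.6.3 keeps the number and drops the distinction.

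**Step 3: who is exposed, and when.**
- At baseline: hormonal contraception, pregnancy and cycle phase. Endocrine therapy is excluded at this point.
- At later draws: the same, plus any endocrine therapy started after registration.

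**Step 4: could exposure differ between the compared groups?** Section 8.6.1 expects contraception use to vary with type of treatment (chemotherapy, RT, surgery or combination) and adjusts the contraception model for it. To the extent that methods are hormonal, the plan's own expectation is that exposure is unbalanced across the contrast in section 8.6.3.

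**Step 5: illustration of size (assumptions, not document figures).** For patients, let p be the true proportion with disruption, h the share whose classification is open to hormonal exposure, fn the chance that exposure hides true disruption, and fp the chance that exposure produces FSH of 23 or more without disruption:

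apparent proportion = p(1 − h·fn) + (1 − p)·h·fp

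Hiding only (fp = 0), p = 80%, h = 30%:
- fn = 10%: 0.80 × (1 − 0.03) = 77.6%
- fn = 30%: 0.80 × (1 − 0.09) = 72.8%

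False cases only (fn = 0), h = 30%:
- p = 80%: 0.80 + 0.20 × 0.03 = 80.6% at fp = 10%; 0.80 + 0.20 × 0.09 = 81.8% at fp = 30%
- p = 30%: 0.30 + 0.70 × 0.03 = 32.1% at fp = 10%; 0.30 + 0.70 × 0.09 = 36.3% at fp = 30%

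Range over h = 10% to 50%, with error chances of 10% to 30%:

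| True p | Error | Apparent range |
|---|---|---|
| 80% | hiding only | 79.2% to 68.0% |
| 80% | false cases only | 80.2% to 83.0% |
| 30% | false cases only | 30.7% to 40.5% |

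**Step 6: against sampling error.** The number receiving chemotherapy is not given; 200 is the ceiling. The exact 95% interval is 73.8% to 85.3% at 160/200, a half-width of (85.3 − 73.8)/2 ≈ 6 points. At 80/100 it is 70.8% to 87.3%. At h = 30% the hiding shift is 2.4 to 7.2 points, so it can exceed the half-width at 200. The reported interval does not reflect it.

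**The case against.** The case on the other side has substance.

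- **Scope.** FSH is one of four markers, each reported separately, in a correlative sub-study closed to accrual since March 10, 2021. Section 1.7 raises the FSH limitation while presenting AMH, which is also measured. This stands, and it limits the importance of the point.
- **Unseen material.** Section 8.1 places endpoint details in Addendum II, and the abstraction and interview items are not in the supplied text. One of these may deal with hormone use. This stands as a caveat. Section 8.6.3 nevertheless states a complete case rule and model for this sub-study and uses no such data.
- **Direction and size.** Section 1.7 gives neither, and it does not mention pregnancy. This stands; including pregnancy among the hormonal states is this review's assumption.
- **Timing.** Draws follow a fixed visit and regimen schedule, and matching them to routine blood work only reduces burden. This stands. The relevant fact is that the schedule is not tied to cycle or hormone use.

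A reader might also infer three stronger things that the documents do not support:

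1. That a true 80% would be declared a failure. Section 8.6.3 has no decision rule against 80%, and the hypothesis names no marker. A large shift would need exposed patients to be masked completely at every counted draw, which no passage says.
2. That the hypothesised Stratum 2 rise in LTC use, from 20% to 60% at 6 months (section 8.5.2), shows how far exposure moves. That rise compares Arm B with Arm A, not chemotherapy with none. Stratum 2 is about 40% of patients and Arm B was 34% of enrolment (section 8.3), so the rise concerns about 0.40 × 0.40 × 0.34 = 5.4% of all patients. Even that assumes every added method is hormonal, which is not stated.
3. That AMH should replace FSH as lead marker. The AMH entries in Table 7 are headed as abnormal but carry a reference-range footnote and need reconciling first.

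**Conclusion.** The point holds, within limits. As written, section 8.6.3 can misclassify patients on FSH and can confound the FSH comparison of chemotherapy with no chemotherapy, for a reason that section 1.7 itself gives. The size is unknown. With 30% of patients exposed and a 10-30% chance of hidden disruption, a true 80% would read as 77.6% to 72.8%; if exposure creates false cases, the error runs the other way. These values rest on assumed exposure and error rates.

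The conclusion does not extend to AMH, TSH or TPO, or to the trial's primary endpoint, and it does not say that the 80% hypothesis would be wrongly rejected. The change is worth making because it is cheap and because the planned interval cannot show this error.

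**What to change.** In section 8.6.3:

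1. Derive a flag at each draw for current endocrine therapy, hormonal contraception or pregnancy, from the pregnancy test, abstraction form and patient interview at the same visit. First confirm that the forms capture these items. Pregnant patients may stop testing until delivery (section 7, Table 1 footnotes), so take continuing pregnancy from the Pregnancy Supplement Form. Say how a form and a draw are matched when their dates differ within the visit windows.
2. Keep the all-draws FSH percentage as planned. Report beside it a prespecified analysis restricted to unflagged draws.
3. Report the FSH mixed model with the flag as a time-varying covariate beside the unadjusted model.
4. State that cycle phase remains uncontrolled unless last menses is recorded.

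The cost is SAP wording and a derived variable, with no extra draws. The restricted analysis has fewer evaluable FSH values and a wider interval. It also selects on treatment received after baseline, which is why it stands beside the all-draws result and does not replace it.

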8.6.4 Plan for Longitudinal Study of Sexuality

Measurement of PROMIS Sexual Function Survey Brief Profile v1.0 - Female will be used to evaluate the hypotheses that (1) cancer survivors' sexual function decreases during primary cancer treatment then increases after treatment completion and (2) cancer survivors have lower levels of satisfaction with their sex lives compared to the age-matched general population at baseline. All patients recruited for the EROS study will be included in this part of analysis. Data collected in PROMIS Sexual Function Survey Brief Profile v1.0 - Female in the EROS study will be summarized and plotted across time with respect to each of the subdomains (global satisfaction with sex life, interest in sexual activity, lubrication, vaginal discomfort, and orgasm). A linear mixed-effect model will be used to study changes in each of the subdomain scores of PROMIS Sexual Function Survey Brief Profile v1.0 - Female over time, with institution as the random effect (by stratum and across all patients if there is no difference between strata). For the secondary hypothesis, our comparative group is the

Rev. Add9

Rev. Add8

age-matched population of non-cancer females in the reproductive age range surveyed by the Duke Clinical Research Institute. The collaborator at Duke Clinical Research Institute will provide summary data on age-matched non-cancer patients. The PROMIS study uses a *T* score method with a mean of 50 and a standard deviation of 10. Results from the Sexual Function Survey in the EROS trial will be transformed into *T* scores as well then comparison between the groups will be performed using the two-sample *t* test.

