5.4 Patient Recruitment

Patients from oncology clinics with newly diagnosed cancer are possible candidates for the study. Complete eligibility criteria are included in Section [3](#). After the diagnosis of cancer is given to the patient, the primary provider will refer the patient to the study personnel for initial contact. The primary provider is defined as the clinician (MD, nurse practitioner, PA-C) that is clinically assessing the oncology patient. Subjects must enroll prior to initiation of chemotherapy or radiation, if applicable.

Institutions will identify a clinical research nurse (CRN)/CRA that will be responsible for all aspects of this study. The designated (CRN)/CRA from each institution will be available to work with physicians during the clinical session to identify and recruit patients. This person will discuss the details of this study with appropriate care and thoughtfulness as she has recently received the diagnosis of a cancer. If the patient agrees, she will be screened for study eligibility at that time or at a subsequent visit as deemed appropriate by study personnel. This person will also be available to answer any questions regarding the study.

Patients will either be enrolled in the study or listed on the “Patient Log” ([Appendix II](#)), which requires a reason for the patient’s decision not to participate. Please keep a copy of the Patient Log in patient chart at institution.

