5.5 Data Collection

Patients will be followed over time and all surveys will be administered as described in Table 1 (Section [7](#)).

Rev. 11/16

- 5.5.1 Following site randomization and local IRB approval, a consent form will be given to each provider (oncology staff, i.e. MD, nurse practitioner or PA-C, that clinically assesses the patient). A signed provider consent form is required for participation.
- 5.5.2 Upon site study activation a delegation of responsibility log should be completed and submitted to CTSU prior to enrolling the first patient
- 5.5.3 Patients will be recruited to participate at their scheduled provider appointment. Study staff will approach patients who are possible candidates to determine interest. If interested, eligibility will be confirmed (Section [3](#)).

Rev. 11/17

- 5.5.4 A consent form will be given to interested and eligible patients. The consent form should be completed on the same day eligibility is confirmed, however, it must be signed prior to treatment initiation (See Section [7](#) Patient-specific timeline).
- 5.5.5 Patient will have the baseline provider visit, complete baseline surveys and be registered to the trial on the same day of consent. If this is not feasible, then all baseline requirements (including registration) must be completed within one week of patient consent. Baseline provider visits, completion of baseline surveys and study registration must be completed on same day. (Table 1).
- 5.5.6 The designated research staff person (CRN or CRA) from each institution will administer questionnaires and assist with the completion of form(s) at the baseline and follow-up visits, as necessary. A CRN or CRA must review form(s) for completeness as

soon as the patient finishes them to ensure all items have been marked appropriately.

- 5.5.7 The scheduled study tools must be completed during the visit.
- 5.5.8 Completed clinician and patient form(s) will be entered into Medidata Rave within 7 days of collection.

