Provider Consent Form	X				
Delegation of Responsibilities Log	X				
CLINICIAN					
Provider Reproductive Health Values Survey (General) ³	X		X		
Provider Reproductive Health Values Survey (Specific to Patient) ⁵		X			X
Medical Record Abstraction Form – Baseline ⁶		X			
Medical Record Abstraction Form – Follow-up ^{6,13}				X	X
Pregnancy Test ⁷		X		X	X
Pregnancy Supplemental Form ⁸		X		X	X
PATIENT					
Patient Baseline Interview ⁹		X			
Sexual Function Survey		X		X	X
Patient Interview - During Chemotherapy/Radiation Treatment ¹⁰				X	
Patient Follow-up Interview ^{11, 12}					X

1. Pre-Study documents should be completed prior to participant recruitment.
2. These documents need to be updated based on staffing and provider changes over the course of this study. We define provider as the clinician (MD, nurse practitioner or PA-C) that clinically assesses the oncology patient.
3. Each primary clinician should complete this form once at 0 (Prior to Study Training) and 30 months from site initiation. It is not necessary to fill out the form for each patient at each of these time points. As staffing changes over the course of this study new clinicians will complete this form

Rev. 11/16

Rev. Add8 upon signing provider consent and at 30 months from site initiation. The date for site initiation is defined as the time when the site is approved to enroll patients into this study.

Rev. Add10 4. Patient will have the baseline provider visit, complete baseline surveys and be registered to the trial on the same day of consent. If this is not feasible, then all baseline requirements (including registration) must be completed within one week of patient consent and before treatment initiation as part of their standard of care (i.e., chemotherapy or radiation therapy). Baseline provider visits, completion of baseline surveys and study registration must be completed on same day.

5. This form should be completed by the primary clinician after each office visit (as determined by the CRN/CRA)

6. Complete the medical record abstraction forms from the medical chart of each eligible participant after visit with the patient. Form must be completed and entered electronically in Medidata Rave within one week of patient visit.

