Rev. Add8	The primary objective of this study is to evaluate the success of implementation of the reproductive health programming among females aged between 15-55 years old with initial diagnosis of any form of cancer (before chemotherapy or radiation has started). Secondary objectives include (1) assessing the degree of discrepancy between patients and their clinicians in estimates of significance of the reproductive health goals for the patient, (2) evaluating baseline and follow-up reproductive health assessments for trends in reproductive health choices relating oncofertility, oncocontraception, and pregnancy over the 2 year study period, (3) identifying clinical and demographic factors that predict the adequacy of reproductive health management.
Rev. Add9	
Rev. Add11	
Rev. 11/17	E1Q11 is a cluster randomized trial (CRT) with patients in one site all receiving the same intervention. This study was originally designed with a paired-matching cluster randomization, paired mainly by the type of institution (MU NCORP vs. NCORP) and geographical region (Northeast vs. Midwest vs. South vs. West). However, this design falls apart as some sites originally invited to participate in this study dropped from the study (at various time points). Consequently, the study design is now changed to a parallel cluster randomization (i.e., with clusters randomized to one of treatment arms). To have a manageable number of patients in this study and have this study completed in a reasonable timeline, the sample size was re-calculated based mainly on the primary endpoint of the primary objective (instead of the important secondary endpoint of the primary objective) and the patient's age limit was lowered to 15 years. Due to an oversight in previous sample size calculations, the sample size was re-calculated in amendment 13.
Rev. Add8	
Rev. Add9	8.1 Design and Randomization

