8.6 Analysis Plan

8.6.1 Plan for the primary objective
With a cluster randomized design, the generalized estimating equations (GEEs) method will be used to evaluate the intervention effect. The GEEs method can be used to construct an extension of standard logistic regression²⁷. For the primary endpoint, appropriate reproductive health management, a GEE model with an exchangeable correlation structure (i.e., assuming every patient within a cluster is equally correlated with every other patient from that cluster) and registering institution as the cluster variable will be fitted to compare the rates between the intervention group and the no intervention group by combining patients in all strata. The appropriate reproductive health management rate at each time point will be summarized, by arm, with frequency and percentage along with its 95% confidence interval. This rate in the non-intervention arm will indicate whether reproductive health needs are adequately addressed (Hypothesis 1, Section [1.4.1](#)). Whether the intervention can improve reproductive health care (Hypothesis 2, Section [1.4.2](#)) can be determined by comparing this rate between the non-intervention arm and the intervention arm.

The same method will be used to evaluate the intervention effect on contraception usage for Stratum 1 and Stratum 2, separately. Since it is expected that contraception usage will be influenced by the number

of children (0, 1-2, >2), type of treatment (chemo vs. RT vs. surgery vs. combination), and disease stage (nonmetastatic vs. metastatic) as well, these factors will be included in the model as covariates. The contraception usage rate at each time point will be reported with frequency and percentage along with its 95% confidence interval. Similar analysis method will be applied to the proportion of patients with pregnancy by the end of 2 years after baseline visit on the study. The analysis will be applied to patients by stratum for each of these secondary endpoints.

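### Patients may register after most kinds of cancer surgery, so the sexual-function baseline can mix pre-treatment and post-surgical scores, and Section 8.6.4 does not separate them

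*Combined protocol and SAP*

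**What the plan says.** **The hypothesis.** Section 8.6.4 examines whether "sexual function decreases during primary cancer treatment then increases after treatment completion". A second hypothesis compares satisfaction at baseline with an age-matched general population. Section 5.7.2 describes the survey as measuring sexual health from diagnosis through treatment.

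**Who may register, and when.**
- Criterion 3.1.2: "Patients must not have initiated chemotherapy, radiation therapy or endocrine therapy prior to registration to this study".
- Criterion 3.1.3: "Patients must not have had a prior hysterectomy, bilateral oophorectomy or sterilization of any method".
- Section 5.4: "Subjects must enroll prior to initiation of chemotherapy or radiation, if applicable".
- Section 5.5.4, on the consent form: "it must be signed prior to treatment initiation".
- Section 7, Table 1, footnote 4, on completing baseline: "before treatment initiation as part of their standard of care (i.e., chemotherapy or radiation therapy").
- Opening of Section 8, on the population: "initial diagnosis of any form of cancer (before chemotherapy or radiation has started").

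**What counts as treatment.** The contraception model in 8.6.1 adjusts for "type of treatment (chemo vs. RT vs. surgery vs. combination").

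**The analysis.** Section 8.6.4 includes every recruited patient in a linear mixed model of change in each subdomain score over time, with institution as the random effect. It is run by stratum, and across strata if they do not differ. Scores are T scores with SD 10.

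**The concern.** A hypothesis that function falls during primary treatment and recovers afterwards needs a level measured before treatment. The rules supply that level relative to chemotherapy, radiation and endocrine therapy only. A woman who has already had, say, breast or bowel surgery can register, and her first survey is labelled baseline. If more treatment is to follow, that survey sits part-way through primary treatment. If surgery is all she receives, it comes after treatment has ended and she has no earlier measurement.

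Two things are at stake. Pooling such baselines with true pre-treatment ones shifts any baseline-to-treatment contrast, and recovery from surgery may look like a rise from baseline. The same baseline also feeds the comparison with the general population, where a deficit could partly reflect recent surgery. Section 1.2 names the sexual-function study as one of two important secondary objectives.

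**Working it through.** **Step 1: is surgery before baseline allowed?** Criterion 3.1.2 lists three barred treatments, and surgery is not one of them. Section 5.4 and the opening of Section 8 refer only to chemotherapy or radiation. The consent rule in 5.5.4 uses the general term treatment, but Table 1 footnote 4 spells the term out as chemotherapy or radiation. Only 3.1.3 excludes earlier operations, and it names three: hysterectomy, bilateral oophorectomy and sterilization. Section 1.5 expects colorectal, breast and lung cancers, among others, and 3.1.1 admits DCIS. Surgery for those cancers is not excluded.

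**Step 2: does the plan regard surgery as treatment?** Yes. Section 8.6.1 gives it its own treatment category.

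**Step 3: does anything later separate these patients?**
- The strata (8.1) are built on pregnancy or pregnancy intention, sexual activity and completed childbearing, not on treatment.
- The extra survey visits (5.7.2; Section 7, Table 1, footnote 10) are triggered by chemotherapy or radiation, so a surgery-only patient has none.
- The endocrine analysis (8.6.3) splits patients by chemotherapy. Section 8.6.4 has no matching step for surgery.

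**Step 4: how large could the effect be?** The plan states no effect size or power for this hypothesis, so there is no figure to reproduce. An illustration needs three inputs, all assumed here:
- F: true mean fall from the pre-treatment level, in T-score points (3 or 5).
- s: share of patients operated on before baseline (0.1 to 0.7).
- d: points already lost to surgery at baseline (1 to 3, with −1 as the reverse case).

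The mean baseline is lowered by s × d. With the later level held fixed, meaning the surgical loss is still present at the later assessment:

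observed fall = F − s × d

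| F | s | d | Observed fall | Shortfall |
|---|---|---|---|---|
| 5 | 0.1 | 1 | 5 − 0.1 = 4.9 | 2% |
| 5 | 0.3 | 2 | 5 − 0.6 = 4.4 | 12% |
| 5 | 0.5 | 2 | 5 − 1.0 = 4.0 | 20% |
| 5 | 0.7 | 3 | 5 − 2.1 = 2.9 | 42% |
| 3 | 0.1 | 1 | 3 − 0.1 = 2.9 | 3% |
| 3 | 0.7 | 3 | 3 − 2.1 = 0.9 | 70% |

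If scores are higher after surgery (d = −1), the sign flips. A 5-point fall appears as 5.1 (s = 0.1) to 5.7 (s = 0.7), and a 3-point fall as 3.1 to 3.7.

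**The case against.** **The operations closest to the outcome are excluded.** Criterion 3.1.3 removes prior hysterectomy and bilateral oophorectomy, arguably the operations that bear most directly on lubrication and vaginal discomfort. This stands. A reader might infer from 3.1.2 alone that no prior cancer surgery is barred; 3.1.3 shows otherwise. It narrows the gap without closing it.

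**The direction is not established.** A reader might infer that the fall is bound to be understated. The documents do not support that. The protocol's own hypothesis about primary treatment points that way, but Section 1.8 cites work in which fear of intercourse and pain were present before surgery, and reports that many participants described better intimacy after cancer.

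**No fall-from-baseline test is named.** This also stands. Section 8.6.4 speaks of change over time and does not define when treatment begins or ends. The bias therefore attaches to whichever baseline contrast is drawn from the model. Surgery before baseline is one instance of that wider lack of definition.

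**The second hypothesis does not claim to separate diagnosis from surgery.** Correct. A mixed baseline does not contradict it, so reporting by surgery status there is helpful but optional.

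**Other material may cover this.** Section 8.1 places endpoint details in a statistical analysis plan in Addendum II, which is not among the documents reviewed. Whether it deals with this sub-study cannot be told, so the point concerns 8.6.4 as written.

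**It is an observational objective.** Neither the randomized comparison nor the primary endpoint is affected, which limits the weight of the point.

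**Conclusion.** The gap holds. As written, the rules admit patients after most kinds of cancer surgery, the plan counts surgery as treatment, and 8.6.4 pools their baselines with pre-treatment ones without distinguishing them. A baseline-to-treatment contrast used for the first hypothesis is biased whenever surgery has shifted scores: too small if it lowered them, too large if it raised them.

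Confidence in the gap is high and confidence in its size is low. In the illustration the shift runs from 0.1 to 2.1 points, or 0.01 to 0.21 of the T-score SD of 10. These figures rest on assumed values of s, d and F and on the surgical loss persisting. If operated patients recover before the later assessment, the range is not a bound. It should not be read as an estimate for this trial, and the documents do not support any fixed percentage of understatement. This is an inexpensive improvement to a secondary analysis.

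**What to change.** In 8.6.4:

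1. Derive from the medical record abstraction whether cancer surgery preceded the baseline survey.
2. Add that indicator and its interaction with time to the mixed model.
3. Keep the all-patient estimate and report alongside it the baseline-to-treatment change in patients not yet operated on at baseline. The contrast has to be named for either estimate.
4. Optionally, describe the baseline comparison with the reference population by surgery status.

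The unoperated subset should accompany the all-patient result and not replace it, because choosing patients by surgery status also selects cancers and treatment sequences.

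**Cost.** One derived variable and a few lines of text, with no change to eligibility, visits or care. A surgery date must be obtainable from the abstraction form. That form is not in the documents, although 8.6.1 already requires type of treatment. The model carries extra terms, and the subset estimate has a wider interval and a selected case mix.
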